5.3.2.2. Exposure

No imputation will be done for first dose date. Date of last dose of study treatment, if unknown or partially unknown, will be imputed as follows:

- If the last date of study treatment is completely missing and there is no EOT CRF page and no death date, the participant should be considered to be ongoing and use the data cutoff date for the analysis as the last dosing date; or
- If the last date of study treatment is completely or partially missing and there is EITHER an EOT CRF page OR a death date available (on or prior to the data cutoff date), then impute this date as the last dose date:
 - = 31DECYYYY, if only Year is available and Year < Year of min (EOT date, death date),
 - = Last day of the month, if both Year and Month are available and Year = Year of min (EOT date, death date) and Month < the month of min (EOT date, death date), or
 - = min (EOT date, death date), for all other cases.

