2.1.1. Primary Estimand

The primary estimand is the incidence of Adverse Events from the time of first dose to 35 days post last dosing date or the date prior to initiation of a new anticancer therapy, whichever occurs first for all participants who receive at least one dose of lorlatinib, regardless of dosing interruptions or dosing compliance. It includes the following 4 attributes:

 Population: Participants with unresectable advanced and/or recurrent ALK-positive NSCLC with resistance or intolerance to at least 1 prior ALK inhibitor treatment as defined by the inclusion and exclusion criteria, and who receive at least one dose of Lorlatinib

- Variable: Binary indicator of whether any AE occurring at least once
- Intercurrent event: All data after the intercurrent event "initiation of a new anticancer therapy (-1 day)" or "treatment discontinuation (+35 days post last dosing date)" will be excluded. Dosing interruptions or dosing compliance are not considered as intercurrent event for this analysis..
- Population-level summary: Adverse event incidence rate from the time of first dose to 35 days post last dosing date or the date prior to initiation of a new anticancer therapy, whichever occurs first. AE incidence rate is the number of patients with any AE occurring at least once in the study population.

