YYYY = Year of min [max(PD date + 1, last dose of study treatment + 1), end date of new anticancer therapy], AND

MMM = Month of min [max(PD date + 1 day, last dose of study treatment + 1 day), end date of new anticancer therapy]

THEN

imputed start date = min [max(PD date + 1 day, last dose of study treatment + 1 day), end date of new anticancer therapy]);

ELSE IF

YYYY = Year of min [max(PD date + 1, last dose of study treatment + 1), end date of new anticancer therapy], AND

```
MMM > Month of min [max(PD date + 1 day, last dose of study treatment + 1 day), end date of new anticancer therapy]

THEN

imputed start date = 01 MMM YYYY;

ELSE IF

YYYY < Year of min [max(PD date + 1, last dose of study treatment + 1), end date of new anticancer therapy]

THEN

imputed start date = DAY (Last day of MMM) MMM YYYY;

ELSE IF

YYYY > Year of min [max(PD date + 1, last dose of study treatment + 1), end date of new anticancer therapy]

THEN
```

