6.5.3. Study Treatment Exposure

6.5.3.1. Exposure to lorlatinib

Exposure will be summarized for the Safety analysis set.

The summary of treatment exposure for lorlatinib will include the following information:

- Treatment duration (days)
- Cumulative dose (mg)
- Dose intensity (mg/day)
- Relative dose intensity (%).

The duration of lorlatinib (in days) is defined as:

```
Treatment duration (days) = (last dose date - first dose date + 1)
```

The cumulative dose (mg) of lorlatinib is the sum of the actual dose levels that the participant received (i.e., total dose administered (mg)).

The dose intensity (DI) and the relative dose intensity (RDI) of lorlatinib will be calculated for each participant during the study. The DI (mg/day) of lorlatinib during the study is defined as

```
DI(mg/day) = [cumulative dose(mg)]/[treatment duration(days)]
```

The RDI of lorlatinib is defined as the ratio of the DI and planned dose intensity d and expressed in %

RDI (%) =
$$100 \times [DI (mg/day)/[d (mg/day)].$$

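### SAP 5.3.2.2 has no case for a last-dose date with a known month in an earlier calendar year, so the imputed date falls after the recorded month (minor)

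*SAP*

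**What the plan says.** SAP 5.3.2.2 (Exposure) applies its partial-date rule under this condition: "If the last date of study treatment is completely or partially missing and there is EITHER an EOT CRF page OR a death date available". Three cases follow:

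1. Year only: "31DECYYYY, if only Year is available and Year < Year of min (EOT date, death date").
2. Month and year: "Last day of the month, if both Year and Month are available and Year = Year of min (EOT date, death date"), with the further condition that the month is earlier than that of min(EOT, death).
3. Everything else: "min (EOT date, death date), for all other cases".

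Two other rules in the same SAP deal with dates where only the day is missing:

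- SAP 5.3.2.4 (start of new anticancer therapy) has an explicit branch for "YYYY < Year of min [max(PD date + 1, last dose of study treatment + 1), end date of new anticancer therapy"], which gives the last day of the known month.
- SAP 5.3.2.5 (other dates) moves a stop date with a missing day to the end of its month, with no condition on the year.

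The last-dose date is used in several places:

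- SAP 6.5.3.1: "Treatment duration (days) = (last dose date - first dose date + 1") and "DI(mg/day) = [cumulative dose(mg)]/[treatment duration(days")].
- SAP 2.1.1: the primary adverse-event window runs "from the time of first dose to 35 days post last dosing date or the date prior to initiation of a new anticancer therapy", whichever is first.
- SAP 6.1.1.1: deaths within 28 days of last dose.
- SAP 5.3.2.4: imputed start dates of new therapy.

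**The concern.** An imputed date should not contradict the part of the date that the site did record. Here it does, and a fuller entry gives a worse result than a sparser one. Case 2 shows that the authors meant to respect a recorded month, but it stops working when the calendar year changes between last dose and EOT or death.

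The error has one direction, because the imputed last dose is always later than the recorded month allows. At stake are the individual exposure figures, the derived end of the on-treatment period, and membership of the group counted as dying within 28 days of last dose. A programmer who follows the text will reproduce the error.

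**Working it through.** The plan gives no figure to reproduce. The check is of the logic, followed by dates. **All calendar dates below are assumptions**, because the documents report no actual dates and no count of incomplete ones.

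**Logic.** Let R = min(EOT, death). Take an entry with month and year known, and a year earlier than that of R.

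- Case 1 needs only the year to be available. The month is available too, so it fails.
- Case 2 needs the years to be equal. They differ, so it fails.
- Case 3 applies, and the date is set to R, in a later calendar year than the one recorded.

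With R = 20 Jan 2022, the entry 2021 becomes 31 Dec 2021, while the more informative entry Nov 2021 becomes 20 Jan 2022.

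**Coverage.** The three cases were applied as written to every R in two non-leap calendar years, with a recorded month one to six months earlier: 730 × 6 = 4,380 combinations. The year changes in 2 × (31 + 59 + 90 + 120 + 151 + 181) = 1,264 of them. All 1,264 gave a date 1 to 184 days after the end of the recorded month. Every same-year combination stayed inside the recorded month.

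**Treatment duration** = last dose − first dose + 1 (SAP 6.5.3.1). The fix uses the last day of the recorded month.

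| First dose | Recorded last dose | EOT | Duration as written | Duration with fix | Difference |
|---|---|---|---|---|---|
| 1 Mar 2021 | Dec 2021 | 5 Jan 2022 | 311 | 306 | 5 days |
| 1 Mar 2021 | Nov 2021 | 10 Jan 2022 | 316 | 275 | 41 days |
| 1 Aug 2021 | Nov 2021 | 20 Jan 2022 | 173 | 122 | 51 days |
| 1 Mar 2021 | Oct 2021 | 15 Feb 2022 | 352 | 245 | 107 days |

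For the third row:

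- As written: 31 + 30 + 31 + 30 + 31 + 20 = 173.
- With the fix: 31 + 30 + 31 + 30 = 122.

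**Derived 35-day window, third row.**

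- As written: 20 Jan + 35 days = 24 Feb 2022.
- With the fix: 30 Nov + 35 days = 4 Jan 2022.

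**Dose intensity, third row.** Planned dose is 100 mg/day. The result depends on something SAP 6.5.3.1 leaves open, namely how cumulative dose is computed when the end of the last dosing record is imputed.

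- *Cumulative dose fixed.* Assume a true last dose on 15 Nov, so 107 doses or 10,700 mg. Relative dose intensity is 10,700/(173 × 100) = 61.8% as written and 10,700/(122 × 100) = 87.7% with the fix.
- *Dose accrued daily to the imputed date.* Relative dose intensity is 100% either way. Cumulative dose is 17,300 mg as written and 12,200 mg with the fix.

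**The case against.** Most of the case on the other side concerns size, and much of it stands.

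- **The 51-day example needs a late EOT visit.** A last dose on 15 Nov and EOT on 20 Jan are 66 days apart. The Schedule of Activities gives the EOT visit a ±7-day window. If that is read as about a week around the last dose (an assumption), the year-end case is a December last dose with an early-January EOT, as in the 5-day row. This stands for the usual case. Longer gaps remain possible: SAP 3.4 takes the last non-zero dose, protocol Table 2 states no maximum length for a dose hold, and a participant without an EOT page is dated by death.
- **Dose intensity.** A reader might infer that relative dose intensity falls from 100% to 62%. The documents do not support this. The 100% rests on a true stop date that no imputation could recover. The missing case accounts for 88% against 62%, and only if dose is not accrued to the imputed date.
- **The primary endpoint.** A reader might infer that the adverse-event incidence is inflated. Active collection ends 28 to 35 days after the actual last dose (Protocol 8.2). In the example that is 4 Jan 2022 at the latest. After that, SAEs are reported if the investigator learns of them. The window is also cut at new anticancer therapy, and the variable is whether any AE occurred at all. One late event would rarely change that.
- **Rarity.** The day must be missing, the month known, and EOT or death in a later year. Visits fall every 28 days, study drug is accounted for and CRFs are monitored, so no affected participants among about 100 is plausible.
- **Intent.** SAP 5.3.2.4 governs a start date, so the contrast makes an oversight likely but does not prove it.

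None of this removes the gap. SAP 5.3.2.5 covers other dates and does not override the specific rule for last dose.

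**Conclusion.** The gap is real on the plain text: a last-dose date with a known month in an earlier year is imputed after that month. For such a participant treatment duration is overstated, and either relative dose intensity is understated or cumulative dose overstated. The derived 35-day window and the 28-day death count can also shift.

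Severity is minor. Few participants, possibly none, are affected. The error is likely days if EOT follows the planned schedule, and weeks or more if EOT or death is late. The effect on the any-AE rate is probably negligible. The study is single-arm and descriptive, with no hypothesis test or decision rule, so no formal conclusion turns on it. What remains is that individual durations and dose intensities could be visibly wrong in minima, maxima and listings.

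**What to change.** In the second case of SAP 5.3.2.2, widen the condition. With year and month available, use the last day of the recorded month if **either** the year is earlier than that of min(EOT date, death date), **or** the year is the same and the month is earlier than that of min(EOT date, death date). Leave the first and third cases unchanged.

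The cost is one clause in the SAP and one line of code. It needs no new data, alters no other case, and brings the rule into line with SAP 5.3.2.4 and 5.3.2.5.

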5.3.2.3. Date of Death

Missing or partial death dates will be imputed based on the last contact date:

- If the date is missing it will be imputed as the day after the date of last contact
- If the day or both day and month is missing, death will be imputed to the maximum of the full (non-imputed) day after the date of last contact and the following:

o Missing day: 1st day of the month and year of death

o Missing day and month: January 1st of the year of death

5.3.2.4. Date of Start of New Anticancer Therapy

Incomplete dates for start date of new anticancer therapy (drug therapy, radiation, surgery) will be imputed as follows and will be used for determining censoring dates for antitumor activity analyses and in the derivation of the end of on-treatment period. PD date below refers to PD date by investigator assessment.

- The end date of new anticancer therapy will be included in the imputations for start date of new anticancer therapy. If the end date of new anticancer therapy is
 - o completely missing then it will be ignored in the imputations below
 - o partially missing with only year (YYYY) available then the imputations below will consider 31DECYYYY as the end date of the new anticancer therapy
 - o partially missing with only month and year available then the imputations below will consider the last day of the month for MMMYYYY as the end date of the new anticancer therapy

- For participants who have not discontinued study treatment at the analysis cutoff date, last dose of study treatment is set to the analysis cutoff date in the imputations below.
- If the start date of new anticancer therapy is completely or partially missing, then the imputed start date of new anticancer therapy is derived as follows:
 - o Start date of new anticancer therapy is completely missing

Imputed start date = min [max(PD date + 1, last dose of study treatment + 1), end date of new anticancer therapy]

o Only year (YYYY) for start of anticancer therapy is available

IF YYYY < Year of min [max(PD date + 1, last dose of study treatment + 1), end date of new anticancer therapy] THEN imputed start date = 31DECYYYY;

ELSE IF YYYY = Year of min [max(PD date + 1, last dose of study treatment + 1), end date of new anticancer therapy]

THEN imputed start date = min[max(PD date + 1, last dose of study treatment + 1), end date of new anticancer therapy]

ELSE IF YYYY > Year of min [max(PD date + 1, last dose of study treatment + 1), end date of new anticancer therapy]

THEN imputed start date = 01JANYYYY

Both Year (YYYY) and Month (MMM) for start of anticancer therapy are available
 IF

YYYY = Year of min [max(PD date + 1, last dose of study treatment + 1), end date of new anticancer therapy], AND

MMM < Month of min [max(PD date + 1 day, last dose of study treatment + 1 day), end date of new anticancer therapy]

THEN

imputed start date = DAY (Last day of MMM) MMM YYYY;

ELSE IF

YYYY = Year of min [max(PD date + 1, last dose of study treatment + 1), end date of new anticancer therapy], AND

MMM = Month of min [max(PD date + 1 day, last dose of study treatment + 1 day), end date of new anticancer therapy]

THEN

imputed start date = min [max(PD date + 1 day, last dose of study treatment + 1 day), end date of new anticancer therapy]);

ELSE IF

YYYY = Year of min [max(PD date + 1, last dose of study treatment + 1), end date of new anticancer therapy], AND

```
MMM > Month of min [max(PD date + 1 day, last dose of study treatment + 1 day), end date of new anticancer therapy]

THEN

imputed start date = 01 MMM YYYY;

ELSE IF

YYYY < Year of min [max(PD date + 1, last dose of study treatment + 1), end date of new anticancer therapy]

THEN

imputed start date = DAY (Last day of MMM) MMM YYYY;

ELSE IF

YYYY > Year of min [max(PD date + 1, last dose of study treatment + 1), end date of new anticancer therapy]

THEN
```

5.3.2.5. Other Dates

Imputation methods for other partial dates as follows:

imputed start date = 01 MMM YYYY.

- If the day of the month is missing for a start date used in a calculation, the first day of the month will be used to replace the missing date.
- If both the day and month are missing, the first day of the year is used.
- For stop dates, the last day of the month, or last day of the year is used if the day or day and month are missing, respectively.
- If the date is completely missing, no imputation will be performed.

5.3.3. Missing Toxicity Grade of Adverse Events

Prior to Study Treatment: If no toxicity grade is available or the grade is reported as unknown for an adverse event prior to the first study treatment, then Grade 1 will be assumed for purposes of defining a baseline grade.

In summaries which present maximum toxicity grade, the maximum of non-missing grades will be displayed. Missing grade will only be displayed for cases where a participant reported only one event and the grade is missing.

6. ANALYSES AND SUMMARIES

6.1. Primary Endpoint

6.1.1. Adverse Events

6.1.1.1. Main Analysis

Analysis set: Safety: All enrolled participants who take at least 1 dose of Lorlatinib **Analysis methodology**:

- AE incidence rate is the number of patients with any AE occurring at least once in the study population.
- All Adverse Events (AEs) will be coded using the MedDRA.
- All analyses will be based on treatment emergent events unless otherwise specified. Treatment emergent is defined in Section 3.5.1.

Intercurrent events and missing data:

• All data after the intercurrent event "start of subsequent anticancer therapy (-1 day)" or "35 days after treatment discontinuation" will be excluded from summaries but will be listed regardless of dosing interruptions or dosing compliance.

Summaries used for reporting:

- High-level summaries of adverse events (both All Causality and Treatment Related) will include the number and percent of participants with:
 - o Any Adverse Event;
 - o Serious AE;
 - o Adverse Events with CTCAE Grade 3-4;
 - o Grade 5 events;
 - o AEs associated with dose interruptions;
 - o AEs associated with dose reductions;
 - o AEs associated with withdrawal;

Additionally, the number of events reported for each of the categories above will be provided. Each unique adverse event at the PT level for a participant is included in the count. Seriousness, relatedness, toxicity grade, action taken (interruption, reduction, and withdraw) are as reported by the investigator on the adverse event CRF.

- Summaries by System Organ Class (SOC) and PT in decreasing frequency will be provided for:
 - o Treatment Emergent Events by Maximum Toxicity Grade (All Causality);
 - Treatment Emergent Events by Maximum Toxicity Grade (Treatment Related);

- Serious Treatment Emergent by Maximum Toxicity Grade Events (All Causality);
- Serious Treatment Emergent by Maximum Toxicity Grade Events (Treatment Related);

An event will be considered treatment related if the investigator considered the event related to the study drugs or this information is unknown.

Clustered adverse events will be summarized by maximum CTCAE grade and
causality (all-causality and treatment-related) together with other adverse events.
Adverse Events pertaining to each cluster will be summarized separately, by cluster.
The clustered events are described in a list in the product's Safety Review Plan
maintained by the Sponsor.

The following summaries will be provided by PT/Cluster Term (summaries will not include SOC) in decreasing frequency:

- Treatment Emergent Events (All Causality) by Preferred Term and Maximum Toxicity Grade;
- Treatment Emergent Grade 1-2, 3-4 and 5 Events (All Causality) by Preferred Term and Maximum Toxicity Grade;
- Treatment Emergent Adverse Events Associated with Dose Interruptions (All Causality);
- Treatment Emergent Adverse Events Associated with Dose Reductions (All Causality);
- Treatment Emergent Adverse Events Associated with Withdrawal (All Causality);
- Treatment Emergent Adverse Events Associated with Dose Interruptions (Treatment Related);
- Treatment Emergent Adverse Events Associated with Dose Reductions (Treatment Related);
- Treatment Emergent Adverse Events Associated with Withdrawal (Treatment Related);
- o Serious Treatment Emergent Events (All Causality).
- o Serious Treatment Emergent Events (Treatment Related).

Each participant will be counted only once within each SOC, Cluster Term and PT.

As described in section 5.3.3, in case a participant has events with missing and non-missing toxicity grades, the maximum of the non-missing grade will be displayed. Missing grade will only be displayed in the event that only one event has been reported for a participant and the grade is missing.

- Detailed information collected for each AE will be listed with a description of the event, duration, whether the AE was serious, intensity, relationship to study treatment, action taken, and clinical outcome.
- For AEs of special interest as specified in 3.5.2, these analyses will be performed:
 - o Treatment Emergent Events by Maximum Toxicity Grade (All Causality);
 - Treatment Emergent Events by Maximum Toxicity Grade (Treatment Related);
- Regarding deaths, the following analysis will be performed:
 - The frequency (number and percentage) of participants in the safety analysis set who died and who died within 28 days after last dose of study treatment as well as the primary reason for death, will be tabulated based on information from the 'Notice of Death'.
 - The frequency (number and percentage) of participants in the safety analysis set who died within 30 days of first dose of study treatment will also be provided.
 - Date and cause of death will be provided in individual participant data listing together with selected dosing information (date of first / last administration, dose).

6.1.1.2. Additional Analysis

Basic Results

For summaries required for basic results disclosures in the US and EU the following additional summaries will be provided:

- Treatment Emergent Non-Serious Adverse Events by SOC and PT in >5% of participants;
- Treatment Emergent Non-Serious Adverse Events by SOC and PT;
- Treatment Emergent Serious Adverse Events by SOC and PT; and
- Fatal Adverse Events by SOC and PT.

Each of the above summaries will include a count of the number of participants with all causality events and the number of participants with treatment related events.

6.2. Secondary Endpoints

6.2.1. Confirmed OR

Analysis set: Safety: All enrolled participants who take at least 1 dose of Lorlatinib **Analysis methodology**:

• Objective Response Rate (ORR) defined as the percentage of participants with a confirmed best overall response (BOR) of CR or PR according to RECIST v1.1. BOR will be determined based on reported overall responses at different evaluation timepoints by the investigator from the date of treatment start until documented

disease progression or start of new anticancer therapy, according to the following rules:

- CR = at least two determinations of CR at least 4 weeks apart and documented before progression and start of new anticancer therapy
- PR = at least two determinations of PR or better (and not qualifying for a CR) at least 4 weeks apart and before progression and start of new anticancer
- o SD (for participants with at least one measurable lesion at baseline) = at least one SD assessment (or better and not qualifying for CR or PR) ≥ 6 weeks after date of treatment start and before progression and the start of new anticancer therapy
- Non-CR/Non-PD (for participants with only non-target disease at baseline) = at least one Non-CR/Non-PD assessment (or better and not qualifying for CR ≥ 6 weeks after date of treatment start and before progression and the start of new anticancer therapy
- o PD = progression ≤ 13 weeks after date of treatment start and not qualifying for CR, PR or SD
- O Not Evaluable (NE) = all other cases.

Clinical deterioration will not be considered as documented disease progression.

- participants without documented CR or PR will be considered as non-responders
- 95% CI interval for ORR using the Wilson's Score method

Intercurrent events and missing data:

- data on response after subsequent anticancer therapy is administered will be excluded
- participants with death prior to first post-baseline assessment, inadequate baseline
 assessment, new anticancer therapy started prior to first post-baseline assessment, and
 all post-baseline disease assessments missing will also be considered as nonresponders.

Summaries used for reporting:

- The frequency (number and percentage) of participants with BOR of CR, PR, SD, PD, non-CR/non-PD (applicable only to participants with non-measurable disease at baseline), and NE (not evaluable)
- ORR estimated by dividing the number of participants with OR (CR or PR) by the number of participants in the safety set
- corresponding 2-sided 95% CIs

